aining Gains and Coping with cks 60 min. session by ilitation psychologist	 Reading Assignments: Chapter 9 (Effective Problem Solving) Chapter 10 (The End of The Beginning) Topics: Setting Goals Applying your coping skills to problems Relapse Prevention Coping with Pain During Flare-Ups
	leep 60 min. session by ilitation psychologist aining Gains and Coping with cks 60 min. session by

the changes made are substantive.

Blinding Strategy:

Blinding with respect to the lumbar procedures (LRFA vs. simulated LRFA):

- 1. Participants and treating interventional spine providers will be blinded to the status of LRFA vs. simulated LRFA. The PI [name] and [name] will not be blinded, since they are the overseeing study clinicians. Further details are provided below in Table 2.
- 2. For blinding purposes, both LRFA and simulated LRFA will be performed in an identical fashion with the exception of medial branch lesioning, which will not be done in the simulated LRFA group, as described above. Duration and sounds of both the LRFA and simulated LRFA procedures will be similar. Both LRFA and simulated LRFA will apply all safety precautions normally used in our facility such as not using general anesthesia, and the use of both sensory and motor stimulation to avoid incorrect electrode placement (described further below).

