- 4. The patient and the treating interventional spine provider are therefore blinded to the procedural treatment received. We will employ several strategies to ensure patients are not able to determine which intervention they receive based on the sounds and length of the procedure:
 - i. We will enroll only patients who have not had prior LRFA
 - ii. The electrode will remain in place for the full 90 seconds (and repositioned to simulate a second lesion) for each simulated lesion site.
 - iii. We will use a pre-recorded audio recording of an LRFA procedure in order to simulate the sounds made by the machine during the ablation. We will pre-test this recording several times in the pain clinic in advance of the first randomization.
 - iv. We will use a brief period of sensory stimulation during the simulated LRFA lesion as described above.
- 5. In some clinical situations, it may be impossible for a 2nd interventional spine attending to be on hand to complete a LRFA or simulated LRFA procedure, and maintain blinding of the treating interventional spine provider. For instance, a clinical situation may call that provider away or detain

that individual. In such an instance, the treating interventional spine provider will become unblinded.

6. In the event that participants who are randomized to LRFA vs. simulated LRFA subsequently wish to go on to receive the treatment they were not randomized to, or wish to go on to another lumbar-related procedure that for some reason necessitates that the participant become unblinded to the treatment they were randomized to, prior to the end of the 3-month main follow-up period of data collection, we will unblind participants to their treatment status. This will be done by informing the treating interventional spine provider of the procedural treatment received (LRFA vs. simulated LRFA) prior to a clinical appointment with the participant. The Veteran participant and their provider will then have the information needed to confer and make a fully informed decision about the next clinical treatment steps that are most appropriate for the Veteran.

Blinding with respect to CBT treatments (AcTIVE-CBT vs. TBSCE):

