7. It is not possible to blind patients and rehabilitation psychologists to whether or not they are receiving AcTIVE-CBT or TBSCE. To limit the potential for influencing participants' perceptions of the interventions as more or less likely to be effective, participants will not be specifically told which of the AcTIVE-CBT or TBSCE treatments represents the intervention of interest or the control treatment in the current study. They will however have full advance knowledge of what the treatments will actually entail.

Table 2: Blinding Status of Research Staff		
	Blinded/Unblinded and Reason	When blinded
[name] (PI)	Not blinded (main study physician responsible for clinical issues)	N/A
[name]	Not blinded (study physician responsible for clinical issues pertaining to mental health)	N/A
Drs. [name], [name], [name]	Yes; blinded when not acting as the 2 nd interventional spine attending physician (which he/she will be in cases when another spine provider is the treating interventional spine provider ^a)	Entire study, see superscript 'a' to the left
[name]	Not blinded; except when he is acting as the treating interventional spine provider (in which instances he will be blinded ^b)	Entire study⁵
[name]	Blinded and no contact with individual-level study data at any point	Entire study

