5.0 Reporting

Collection of safety information (monitoring) will be performed by the research staff that administer the assessment questionnaires and facilitate data collection, during data collection. Collection of safety information will also include any ad hoc participant-initiated contacts with the study team, and follow-ups by study staff if tracking the course of any potential complications. We will establish a Data Monitoring Committee (DMC) to oversee study safety data. The DMC is described further below.

We will record any potential complications as adverse events (AEs), defined as any untoward medical occurrence that may present during treatment, but which does not necessarily have a causal relationship with this treatment. We will also record serious adverse events (SAEs). We will complete an AE adverse events form for any AEs that occur during the course of this trial. We will record each event as it happens (or as soon as it becomes known to study research team) and we will follow the AE in subsequent scheduled/completed monthly assessments until resolution, the end of the patient's participation or study completion (whichever occurs first). Study staff will report all AEs to the study PI within 1 business day of learning of the AE. Study staff will also report AEs to the appropriate clinical treating provider (the interventional spine physician for AEs possibly related to medical issues or procedural issues, and the treating psychologist for AEs possibly related to mental health). Study staff will complete and send the AE CRF to the Study PI within 5 business days of learning of the AE. The study staff will be responsible for entering the AE data into the study database within 5 business days of learning of the AE. The study staff will be responsible for entering the AE data into the study database within 5 business days of learning of the AE. Study staff will report the AE to the IRB. AEs will be reported to the IRB at the time of continuing reviews. If appropriate, AEs will be reported to the DMC (as described further below).

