A serious adverse event (SAE) is defined as any untoward medical occurrence that:

- Results in death
- Is life-threatening (Note: the term life-threatening in the definition of "serious" refers to an event in which the patient was at risk of death at the time of the event; it does not refer to an event which hypothetically might have caused death if it were more severe).
- Requires inpatient hospitalization or prolongation of existing hospitalization.
- Results in persistent or significant disability/incapacity.
- Results in congenital anomaly/birth defect (if exposure to a medical product prior to conception or during pregnancy may have resulted in an adverse outcome in the child).
- Requires intervention to prevent permanent impairment or damage.
- Important medical events that may not result in death, be life-threatening or require hospitalization may be considered a SAE when, based on appropriate medical judgment, they may jeopardize the patient and may require medical or surgical intervention to prevent one of the outcomes listed in this definition.

In the proposed trial, the following events are **considered SAEs**:

- Neurologic: paralysis, stroke, central nervous system infection
- Serious hypersensitivity: anaphylactic reactions
- Death
- An event that is life threatening, is permanently disabling, or requires inpatient hospitalization

Severity of adverse event grading scale:

- Mild: an experience that is usually transient, and requires no special treatment or intervention
- Moderate: an experience that is alleviated with simple therapeutic treatments
- Severe: an experience that requires more than simple therapeutic interventions

Relationship to research participation AEs:

- Unrelated This causal relationship is assigned when the AE is definitely not associated with the research participation/treatment
- Unlikely This causal relationship is assigned when there is no temporal relationship to the administration of the investigational material or other factors are more likely to have caused the

event.

- Possibly related This causal relationship is assigned when the AE starts at a reasonable time after study participation but could have been produced by the subject's clinical state or other modes of therapy administered to the subject.

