The study PI will review all AEs to determine study relatedness and outcome of the event. If the PI is not available, AEs that are more pertinent to medical issues or procedures will be reviewed by [name] or [name], and AEs that are more pertinent to mental health will be reviewed by [name].

C. Other reporting

We will complete an AE CRF for any AEs that occur during the main 3-month follow-up period of data collection. We will record each event as it happens (or as soon as it becomes known to study research team) and we will follow the AE at subsequent scheduled/completed monthly assessments, the end of the patient's participation in the study or study completion, or until directed by the participant's treating provider (treating interventional spine provider or treating psychologist) that the AE has resolved or further tracking is not needed (whichever of these occurrences happens first). Study staff will report all AEs to the study PI within 24 hours of learning of the AE. Study staff will complete and send the AE CRF to the Study PI within 5 business days of learning of the AE. The study staff will be responsible for entering the AE data into the study database within 5 business days of learning of the AE. Study staff will requirements for the reporting AE (see below including UAPs), will report the AE to the DMC and/or IRB.

Unanticipated problems (UAPs) are any problem that is 1) unexpected given the research procedures and subject population, 2) related or possible related to participation in the research, and 3) that may have placed participants at a greater risk of harm than was previously recognized. Harm can be further classified as potential harm or actual harm. The study team and/or PI will report any UAPs to the IRB within 5 business days of learning about the AE that was later classified as a UAP. If serious, we will report this using the form " Report of Unanticipated AND Related Serious Adverse Event (SAE), Unanticipated AND Related Adverse Device Effect (ADE), and/or Unanticipated AND Related Problem Involving Risk to Subjects or Others (UPIRTSO)" (Attachment W – Serious Adverse Event Form). UAPs encompass 'unexpected AEs' and are reported similarly. The DMC will review UAPs that are serious at their meetings.

All AEs, UAPs, and SAEs will be clinically reviewed by a study physician (Drs. [name], [name], [name], or [name] as described above) and clinically evaluated and treated as needed, depending on the problem at hand.

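### Section 5.0 gives two incompatible rules for when tracking of an unresolved adverse event stops, so its duration, final outcome and possible upgrade to SAE can go unrecorded

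*Combined protocol and SAP*

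**What the plan says.** The opening text of Section 5.0 Reporting says that each AE is followed at the monthly assessments "until resolution, the end of the patient's participation or study completion (whichever occurs first"). Treating providers are told of AEs, but they have no power to end follow-up.

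Section 5.0, part C (Other reporting), covers AEs in the main 3-month period. It repeats end of participation and study completion as stops and adds another, which either the psychologist or the spine provider who treats the participant can trigger by stating "that the AE has resolved or further tracking is not needed (whichever of these occurrences happens first"). Under this wording, resolution counts when the provider declares it. The provider may also end tracking of an AE that has not resolved.

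Three other parts of the protocol bear on the point:

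- **Persistence.** Section 5.0, part A lists among the SAE criteria: "Results in persistent or significant disability/incapacity".
- **Blinding.** Section 5.1, Blinding Strategy, says by default: "Participants and treating interventional spine providers will be blinded to the status of LRFA vs. simulated LRFA". Item 5 covers the case where no second attending physician is available: "In such an instance, the treating interventional spine provider will become unblinded". Under item 6 the treating spine provider is told the allocation when a participant seeks a further procedure before month 3. For the behavioral factor, item 7 says: "It is not possible to blind patients and rehabilitation psychologists to whether or not they are receiving AcTIVE-CBT or TBSCE".
- **Routing.** The opening text of Section 5.0 sends medical and procedural AEs to the spine physician and mental-health AEs to the psychologist.

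**The concern.** Staff cannot obey both rules for an AE that the participant still has but the provider considers not worth following. Part C sets no threshold for that judgment and asks for neither a reason nor a status when tracking stops.

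Duration matters in this protocol's own terms. The risk description in Section 5.1 separates numbness or weakness that lasts minutes to hours from permanent forms, and it expects procedure-related side effects to be mostly short-lived. The SAE definition turns partly on persistence, and event outcome is one of the minimum items collected for a reported AE (Section 5.0, part B). If tracking ends while the event is present, the record may not show how long it lasted, how it ended, or whether it came to meet the persistence criterion.

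**Working it through.** The plan states no figure on this point, so the check is a comparison of texts, followed by a check of whether the planned safety comparison could move.

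**1. The two rules for an AE reported at month 1 and still present**

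| | Opening text of 5.0 | 5.0, part C |
|---|---|---|
| Stops at resolution | Yes | When the provider directs that it has resolved |
| Stops at end of participation or study completion | Yes | Yes |
| Stops while unresolved, on the provider's direction | No | Yes |
| Criterion, reason or status required at that stop | Not applicable | None stated |
| Main-period assessments with directed follow-up still due | 2 (months 2 and 3) | Possibly 0 |

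The rules conflict only in the third row, and there the conflict is direct.

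**2. What does not depend on continued tracking**

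- Every main-period AE gets a report form (part C), due to the principal investigator within 5 business days.
- The principal investigator determines relatedness and outcome for all AEs (part B), and a study physician reviews them clinically (part C).
- AE questions recur at months 1, 2 and 3 (Section 5.5, Table 5) and cover the time since randomization. They include an open question on other complications (5.0, part B).
- Records are checked monthly for listed SAEs (5.0, part B).

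**3. Where those safeguards fall short**

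- The form will often be complete before persistence can be known.
- The investigator can judge outcome only from what was collected.
- The prompted AE items are surgery, emergency visits, hospital and intensive-care admissions, and allergic reactions. Lingering numbness or pain would have to come up through the open question, and no text says that a repeat report reopens a closed AE.
- The record check lists permanently disabling events, which is narrower than the persistence criterion in part A, and it needs the problem to appear in the record.

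**4. Effect on the planned comparison**

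Section 5.0, part D compares event rates between groups by Fisher's exact test. An AE enters the count once its form is completed, so ending tracking early changes AE incidence by zero. Only an SAE upgrade missed by every route in step 2 could change a count.

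To illustrate, assume 20 completers split evenly on one factor, 10 versus 10. With k events in one arm and none in the other, the two-sided p is 2 × C(10,k)/C(20,k):

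- k = 1: 2 × 10/20 = 1.0
- k = 4: 2 × 210/4,845 = 0.087
- k = 5: 2 × 252/15,504 = 0.033

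The pattern holds from 8 per arm (the minimum of 4 per cell, two cells) to 15 per arm (30 recruited and all randomized). Over that range, k = 1 gives 1.0, k = 4 gives 0.077 to 0.100, and k = 5 gives 0.026 to 0.042. One missed upgrade would not be visible in the test. Part D asks for these comparisons to be read qualitatively, so a single SAE could still matter to the Data Monitoring Committee (DMC).

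**5. Who can end tracking, and what they know**

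The psychologist always knows the behavioral arm, but receives mental-health AEs. The spine provider receives procedural AEs and is blinded, except under items 5 and 6 of the Blinding Strategy. The documents give no frequency for either exception.

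**The case against.** The strongest reply is that this is a wording inconsistency with little consequence. Every main-period AE is recorded and counted. The treating provider does not score it; the principal investigator does. Participants are asked about AEs since randomization every month whether or not an earlier AE was closed, can telephone at any time, and have their records checked. Where a participant changes treatment early, an interim assessment with AE reporting is offered (Section 5.5). No analysis of AE duration or persistence is planned.

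Most of this stands, and it rules out two stronger readings.

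- A reader might infer that persistent harms go uncounted. They do not: the report form, the investigator's review and the Fisher comparison all include them.
- A reader might infer a general between-arm bias in the safety comparison, driven by unblinded providers. The documents do not support that. Weakness, numbness and pain flares go to the spine provider, who is blinded by default. The psychologist's knowledge of arm bears on mental-health AEs.

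It is also fair to say that removing the provider's stop does not make outcome assessment blind, because the principal investigator is unblinded by design (Table 2).

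The reply does not remove the contradiction, and it does not close the gaps in step 3 of the working. The safeguards allow an unresolved AE to resurface, but they do not require that its duration, final status or persistence be recorded.

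**Conclusion.** The point holds in a narrow form, and its severity is minor. Two parts of Section 5.0 give incompatible stopping rules for the same main-period AEs. Under part C, the duration, final outcome and possible SAE upgrade of an unresolved AE can go unrecorded. Occasionally this could happen on the direction of a provider who knows the arm: the psychologist for mental-health AEs, or the spine provider in the two stated exceptions.

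The effect on AE incidence is nil. The number of AEs whose later course would be lost is unknown, because the documents give no closure rate. A reader might divide one event by about 10 participants per arm and infer a shift of 10 percentage points. That figure should not be used: the plan analyzes no proportion of persistent AEs, and one in ten is the weight of any single event in a trial of this size.

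The conclusion assumes that the AE form and survey attachments, which are not in the reviewed text, contain no rule that reopens a closed AE or requires its final status.

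**What to change.** Reconcile the opening text of Section 5.0 and part C into one data-collection rule:

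1. Ask about each open AE at the already scheduled monthly assessments until it resolves, participation ends or the study completes.
2. Record the treating provider's opinion, but do not let it end data collection. Clinical care of the event is unaffected.
3. Record status at last contact as resolved, ongoing or permanent.
4. For every AE still ongoing at month 3, re-check the SAE criterion on persistent or significant disability.

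The cost is wording in two places and a status field on the AE form. No visits are added, because the monthly contacts already take place. The downside is a few more questions about minor lingering complaints.

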6.0 Privacy and Confidentiality

The study will use participants' Protected Health Information (PHI) for the purposes of participant payment by mailed checks to the participant's current address. Also, PHI will be used to contact participants via telephone (as outlined above). PHI will be contained in the crosswalk file that links participant identifiers with the study-specific StudyID. No PHI will be disclosed as part of this study.

We will take multiple steps to protect participants' privacy, confidentiality, and inappropriate disclosure of data, under strict VA security guidelines. All study staff will maintain current on required VA trainings for privacy and confidentiality. Data will be stored in Participant Data Files that will be de-identified, labeled with a code number that is unique to each patient in the study ('study-specific StudyID'). The study-specific StudyID will be a unique numerical code consecutively numbered in order of approach/screening. We will NOT include any protected health information (PHI) in the Participant Data Files. The Participant Data Files will be stored in a secure password-protected electronic location on the VA servers (expected to be the in the J: drive on the Health Services Research & Development (HSR&D) server), accessible only to study staff members and authorized personnel. Staff will maintain a Master List key code that links participants with the study-specific StudyID. This Master List key code will be stored in a secure password-protected electronic location on the VA servers, separately from all other study data. All hard copy participant data will be stored in locked filing cabinets in the locked/secured offices of the Seattle ERIC, while all electronic data will be stored in password-protected files in a limited access folder (to research staff) on a secure VA network drive. Only IRB-approved study personnel will have access to Participant Data Files or Informed Consent Forms. We will only analyze data that does NOT contain PHI, and will report participant data in aggregate form only- no PHI will be entered into analyses or reports.

7.0 Communication Plan

This section is not applicable since this is a single-site study.

VA Puget Sound IRB Protocol Template – Version 1.0: 04/2018

8.0 Information Security and Data Storage/Movement

- Data would only remain within the VA, and would not be moved outside the VA.
- Any hard-copy documents involved will be stored in locked file cabinets in the locked/secured offices of the Seattle ERIC. These will be retained for six years after study closure, until destroyed in accordance with VA procedures, and will not be moved from the ERIC, since there is no need for movement of the documents.
- Similarly, the electronic databases described above in section 7.0 will not be moved. These will be retained for six years after study closure, at which time they will be destroyed in accordance with VA procedures. We will update the above plan as needed if VA procedures and requirements change in the future.

